Individual data listings will be prepared for all data collected.

Further details can be found in Section 8 of the main body of the protocol.

Table 1: Schedule of Study Procedures – Induction and Extended Induction Studies

Procedures	Screening Period		INDUCTION VISITS				EXTENDED INDUCTION VISITS ⁽³³⁾			Early Study Drug D/C ⁽⁵⁾	End of Study (4 weeks post last study dose)
			Day 1	Week 2	Week 4	Week 8a ⁽¹⁾	Week 8b ^{(2),(3)}	Week 12 ⁽²⁾	Week 16 ⁽²⁾⁽⁴⁾		
Study Day/Week	Day -28 to - 1										
	Stage 1	Stage 2									
Window				± 3 days	± 3 days	-3 to + 5 days	+ 1 to 7 days from week 8a visit ⁽⁶⁾	-3 to + 5 days	-3 to + 7 days	+ 5 days	-3 to + 5 days
Informed Consent	X										
Review Inclusion/Exclusion Criteria	X	X	X				X				
Medication and Medical History	X										
Smoking Status			X								
Height	X										
Weight	X		X			X ⁽²⁹⁾		X	X	X	X
Vital Signs ⁽⁷⁾	X		X ⁽⁸⁾	X	X	X ⁽²⁹⁾		X	X	X	X
12-Lead ECG ⁽⁹⁾	X		X ⁽³²⁾			X ⁽²⁹⁾			X	X	X
Physical Examination ⁽¹⁰⁾	X		X	X	X	X ⁽²⁹⁾			X	X	X
Chest X-Ray or equivalent chest imaging	X ⁽¹¹⁾										
Tuberculosis Test (QuantiFERON) ⁽¹²⁾	X										
Plasma PK Samples ⁽¹³⁾			X		X		X	X	X		

Table 1: Schedule of Study Procedures – Induction and Extended Induction Studies

Procedures	Screening Period		INDUCTION VISITS				EXTENDED INDUCTION VISITS ⁽³³⁾			Early Study Drug D/C ⁽⁵⁾	End of Study (4 weeks post last study dose)
			Day 1	Week 2	Week 4	Week 8a ⁽¹⁾	Week 8b ^{(2),(3)}	Week 12 ⁽²⁾	Week 16 ^{(2),(4)}		
Study Day/Week	Day -28 to - 1										
	Stage 1	Stage 2									
Window				± 3 days	± 3 days	-3 to + 5 days	+ 1 to 7 days from week 8a visit ⁽⁶⁾	-3 to + 5 days	-3 to + 7 days	+ 5 days	-3 to + 5 days
Overnight Fasting Lipid Panel	X ⁽¹⁹⁾		X		X	X ⁽²⁹⁾		X	X	X	X
[REDACTED]	[REDACTED]		[REDACTED]	[REDACTED]	[REDACTED]	[REDACTED]		[REDACTED]	[REDACTED]	[REDACTED]	[REDACTED]
Fecal Sample for stool infectious analysis ⁽¹⁴⁾	X										
[REDACTED]			[REDACTED]			[REDACTED]			[REDACTED]	[REDACTED]	
Serology Panel ⁽¹⁶⁾⁽¹⁹⁾	X										
Pregnancy Test (females of child-bearing potential only) ⁽¹⁷⁾	X ⁽¹⁹⁾		X	X	X		X	X	X	X	X
FSH ^{(18) (19)}	X										
Chemistry, Hematology	X ⁽¹⁹⁾		X	X	X	X ⁽²⁹⁾		X	X	X	X
Urinalysis	X ⁽¹⁹⁾		X			X ⁽²⁹⁾			X	X	X
Whole Blood and Serum Biomarker Samples	X		X		X	X ⁽²⁹⁾		X	X	X	X
Genetic Blood Sample (optional – only collected for subjects who provide genetic testing consent)			X								

Table 1: Schedule of Study Procedures – Induction and Extended Induction Studies

Procedures	Screening Period		INDUCTION VISITS				EXTENDED INDUCTION VISITS ⁽³³⁾			Early Study Drug D/C ⁽⁵⁾	End of Study (4 weeks post last study dose)
			Day 1	Week 2	Week 4	Week 8a ⁽¹⁾	Week 8b ^{(2),(3)}	Week 12 ⁽²⁾	Week 16 ^{(2),(4)}		
Study Day/Week	Day -28 to - 1										
	Stage 1	Stage 2									
Window				± 3 days	± 3 days	-3 to + 5 days	+ 1 to 7 days from week 8a visit ⁽⁶⁾	-3 to + 5 days	-3 to + 7 days	+ 5 days	-3 to + 5 days
Endoscopy and Biopsies		X ⁽²⁰⁾				X ⁽²¹⁾			X ⁽²¹⁾		
Concomitant Medication review ⁽²²⁾	X		X	X	X	X	X	X	X	X	X
Adverse Events Assessment ⁽²³⁾	X	X	X	X	X	X	X	X	X	X	X
[REDACTED]	[REDACTED]		■	■	■	■		■	■	■	■
Partial Mayo score		X									
Adapted Mayo score			X ⁽³¹⁾			X ⁽³¹⁾			X ⁽³¹⁾		
Dispense Subject Diary ⁽²⁵⁾	X										
Subject Diary Completion and Compliance Review ⁽²⁶⁾		X	X	X	X	X	X	X	X	X	X
[REDACTED]			■			■			■	■	
[REDACTED]			■			■			■	■	
[REDACTED]			■			■			■	■	
[REDACTED]			■			■			■	■	
Randomization			X ⁽²⁷⁾								

Table 1: Schedule of Study Procedures – Induction and Extended Induction Studies

Procedures	Screening Period		INDUCTION VISITS				EXTENDED INDUCTION VISITS ⁽³³⁾			Early Study Drug D/C ⁽⁵⁾	End of Study (4 weeks post last study dose)
			Day 1	Week 2	Week 4	Week 8a ⁽¹⁾	Week 8b ^{(2),(3)}	Week 12 ⁽²⁾	Week 16 ^{(2),(4)}		
Study Day/Week	Day -28 to -1										
	Stage 1	Stage 2									
Window				± 3 days	± 3 days	-3 to + 5 days	+ 1 to 7 days from week 8a visit ⁽⁶⁾	-3 to + 5 days	-3 to + 7 days	+ 5 days	-3 to + 5 days
Study Drug Dispensing			X	X	X		X				
In Clinic Dosing - Study Drug Dosing ⁽²⁸⁾			X		X		X		X		
Non-Site Study Procedures (Calculations for Programming/Statisticians and applicable suppliers)											
partial Mayo score and PRO2 scores calculation		X	X	X	X	X		X	X	X	X
adapted and total Mayo score calculations			X			X			X		

Abbreviations: D/C, discontinue; ECG, electrocardiogram; EOS, End of Study; FSH, follicle stimulating hormone; [REDACTED]; PK, pharmacokinetic; PRO2, two-item patient reported outcome; [REDACTED]; [REDACTED]; EOS, End of Study

Induction Studies:

¹ Subjects will continue on study drug at the same Induction dose until they return to clinic for **post-central read endoscopy results visit**. Depending on the week 8a adapted Mayo score (using centrally read endoscopy), the subject will proceed with one of the following:

- **Week 8b** visit if subject **did not achieve clinical response**, or
- **Maintenance Week 0** (mWeek 0) if subject **achieved clinical response** (see Table 2 Maintenance Phase Schedule of Study Procedures)

Subject to be reminded not to take study drug on the morning of this next clinic visit, whether Week 8b or mWeek 0, to allow for re-randomization and initiation of study drug of either Extended Induction or Maintenance Study, whichever he or she qualifies for

- ² Week 8b, Week 12, and Week 16 visits pertain only to subjects who undergo extended induction (i.e., who do not demonstrate clinical response based on the adapted Mayo score from Week 8a visit)
- ³ Subject should be instructed not to take study drug from their Induction study drug bottles at home to allow for re-randomization and to receive the first dose of extended induction in the clinic.
- ⁴ Week 16 visit may be done over a period of 1 to 3 visits to complete: a) the Week 16 endoscopy, b) Week 16 clinical assessments (e.g., vital signs, weight, laboratory testing, and Quality-of-Life assessments), and c) an optional visit to bring subjects back (or could be done over the phone) to inform them that they should stop study drug and proceed to EOS visit if they did not achieve clinical response (those who achieve clinical response will proceed to mWeek 0 visit). [REDACTED]
- ⁵ Early Study Drug Discontinuation visit is for subjects who prematurely discontinue the Study drug during the Induction Study. Visit to be conducted within 5 days of the last dose of Study drug, if possible. Subject will also return for the EOS visit for collection of safety data and assessment of disease activity four weeks after last study drug. An EOS visit will be required for all subjects 4 weeks following their last dose of study drug, regardless if they completed the full duration of study drug treatment.
- ⁶ Seven-day window provided to allow time to receive results from the central reading of endoscopy performed at Week 8a.
- ⁷ Blood pressure and heart rate will be measured after the subject has been resting for at least 5 minutes in the seated or supine position. Vital sign measurements should be obtained prior to scheduled blood draws.
- ⁸ Obtain blood pressure and heart rate any time pre-dose at all visits and approximately 1-hour post-dose (any time ≥ 1 hour and < 2 hours) on Day 1 only.
- ⁹ ECGs should be performed after the subject has been resting in a supine position for at least 10 minutes.
- ¹⁰ Physical Exam will be performed as per local standard practice (Section 6.4.1.9).
- ¹¹ A chest X-ray will be performed at screening to assess for signs of latent or active TB or other active viral, fungal or bacterial infections unless one has been performed within 90 days of screening, documented to be negative, and reviewed by investigator. Posterior anterior (PA) and lateral views (lateral view may not be necessary if PA view is deemed adequate by the investigator) will be obtained. Subjects who have had a chest X-ray or equivalent chest imaging within 90 days prior to screening will not require a repeat X-ray unless subject is deemed to be at high risk of recent pulmonary infection. If a chest X-ray is indicated, it may be performed anytime between Screening Stage 1 and Screening Stage 2 visits.
- ¹² Subjects who have had a documented chest X-ray or equivalent chest imaging or TB testing within 90 days prior to Screening do not require a repeat X-ray or TB testing, respectively, unless subject is deemed by the investigator to be at high risk of recent pulmonary infection. Subjects with a history of latent TB should not have a TB test but must not live in a region with high prevalence of multidrug-resistant TB and have completed a well-accepted treatment regimen (e.g., a ≥ 9 -month course of INH or equivalent therapy) within 5 years (3 years in countries where TB is endemic) prior to Screening, the documentation for which must be included in the source document. Subjects who had treated active TB must still have a TB test. Subjects who has a history of latent or active tuberculosis (TB) may be eligible for the Study if criteria outlined in Section 6.4.1.11 are met.
- ¹³ PK sampling will be performed in subjects at the following time points:
- **Day 1 (n= 3 samples):** one sample collected **pre-dose** (within 1 hour prior to study drug administration) and one sample collected **anytime between 0.25 to 0.5 hours post-dose**; and one sample collected **anytime between 1 to 6 hours post-dose**;
 - **Week 4 (n= 2 samples):** one **pre-dose** and one **post-dose** sample collected **anytime between 1 to 6 hours post-dose**
 - **Week 8b (n = 2 samples):** one **pre-dose** and one **post-dose** sample collected **anytime between 1 to 6 hours post-dose**; samples may be obtained up to -7 days from the Week 8a endoscopy visit, but cannot be obtained within 24 hours of endoscopy prep
 - **Week 12 (n= 1 sample):** One sample to be collected **anytime between 0.5 to 6 hours post-doses**

- **Week 16 (n=2 samples):** one **pre-dose** and one **post-dose** sample collected **anytime between 0.5 to 6 hours**. The Week 16 sample may be obtained -3 to + 7 days from the endoscopy visit
NOTE: Post-dose sampling times are defined relative to the time of Study drug administration on the day of collection. All PK sampling times will be accurately recorded by collection date, hour, and minute. Study drug dosing time on the day before each PK collection will also be accurately recorded by dosing date, hour, and minute by the subject; Study drug dosing time on the day of each PK collection will be accurately recorded by dosing date, hour, and minute by the Study staff.
- 14 For stool infectious analysis: Including *C. difficile*, other bacterial pathogens (including *Shigella*, *Salmonella*, *Yersinia*, *E. coli* O157, and *Campylobacter*), and ova and parasite. This can be done **any time after written consent and prior to Screening Stage 2 visit, and results reviewed before Screening Stage 2 visit.**
- 15 [REDACTED]
- 16 Serology testing: Subjects with positive hepatitis B core antibody will undergo testing for hepatitis B DNA and hepatitis B surface antibody during Screening. Subjects with known hepatitis C will also undergo testing for hepatitis C RNA viral load (Refer to Section 6.4.1.18 for details on Serology testing). Serologies do not need to be repeated during re-screening if results from the first screening were negative and within 90 days of re-screening.
- 17 B-hCG testing (serum for Screening and urine for all other visits) will be performed for females of childbearing potential to confirm absence of pregnancy. If urine b-hCG test is positive, confirm with serum b-hCG test.
- 18 Required for postmenopausal females.
- 19 Screening Labs including urinalysis may be obtained anytime during the 28-day window for Screening, but results must be available before Screening Stage 2 endoscopy with the exception of [REDACTED] and fasting lipid panel. *NOTE: Subjects **must not** be requested to come in fasting for study specific assessments prior to signing the informed consent. Exception: The overnight fasting lipid panel may be obtained on Day -28 if subjects are fasting as per institutions standard of care procedure, which must be clearly documented in the source documents.
- 20 Endoscopy with biopsies will be performed at the Screening Stage 2 visit after subject's eligibility from Screening Stage 1 is confirmed. This screening endoscopy must occur at **≥ 5 days before Day 1 to allow ≥ 3 days of symptom reporting for adapted Mayo score calculation on Day 1.** This Screening Stage 2 endoscopic subscore, determined by central reading, will be used to calculate any clinical score for Day 1 that requires the endoscopic subscore. The centrally read endoscopic subscore will be used for all endpoints and for eligibility criteria to enroll a subject into the Induction and Maintenance Studies. Local reading of the endoscopic subscore will also be collected. The aMS will be calculated by the electronic tablet at all applicable visits.
- 21 Centrally read endoscopic subscore from Week 8a visit will used to calculate adapted Mayo score to determine whether subject should undergo extended induction or continue into Maintenance Study depending on whether the subject meets criteria for clinical response at Week 8a. Centrally read endoscopic subscore from Week 16 visit will used to calculate adapted Mayo score to determine whether subject should continue into Maintenance Study or discontinue study drug and proceed to EOS visit depending on whether the subject meets criteria for clinical response at Week 16. Local reading of the endoscopic subscore will also be collected.
- 22 All concomitant UC and non-UC medications (i.e., Prescription and over-the-counter medications, herbals, vitamins, and supplements) that were used within 60 days of screening, including name of medication, date started and stopped, route of administration, indication, and dose will be recorded.
- 23 AE assessments are to include collection and reporting of AEs, SAEs, and AEs of Special Interest (AESIs). Please refer to protocol Section 7 for further details.
- 24 PGA from Screening Stage 1 visit will be used for the partial Mayo score calculation as a guide to assess if subject should proceed with endoscopy at Screening Stage 2 visit. It is suggested that subjects with a partial Mayo score ≥ 3 (reflecting disease that is **at least moderate in severity**) should proceed

with endoscopy screening. This partial Mayo Score can be assessed at any time between Screening Stage 1 visit and Screening Stage 2 visit as long as there are **≥ 3 days of symptom reporting**. The pMS is calculated by the electronic tablet at the Screening Stage 2 visit page and it is recommended that this is completed before the subject proceeds with the Screening Stage 2 visit endoscopy.

- 25 Subjects will be provided with an electronic diary at the Screening (Stage 1) visit and instructed on diary completion, including symptom monitoring and Study drug dosing details. Diaries of symptoms will be collected daily from Screening through the EOS visit.
- 26 Diary completion will be monitored for completeness at each Study visit. Subjects will be counseled on missed Study drug doses and missed diary entries. Subjects who discontinue study drug early due to AE are permitted to optionally complete their daily diary through to the EOS visit.
- 27 Subject will be randomized on Day 1 after all pre-dose procedures have been completed and subject is confirmed to be eligible for the Study. The adapted Mayo score criteria for randomization on Day 1 may be calculated within 48 hours of Day 1.
- 28 Study drug administration will be in-clinic on Day 1, Week 4, Week 8b and Week 16. All study procedures must be done prior to drug administration with the exception of the **post-dose PK sample** and [REDACTED] **samples**. Refer to **footnote 13** for the post-dose instructions for PK collections and **footnote 15** for the [REDACTED] collection window. All other days, subjects will take study drug at home for the rest of the Induction period.
- 29 Procedures may be done -3 to +7 days after week 8a visit (i.e., at the next visit, either Week 8b or mWeek0).
- 30 [REDACTED]
- 31 The adapted Mayo Score at these visits will be calculated by the electronic tablet using the symptoms in the applicable days prior to Day 1, Week8a or Week 16 and the centrally read endoscopy score. This will be available once the centrally read endoscopy score has been received by the site and entered into the electronic tablet.
- 32 ECG at Day 1 is only required during the Phase 2b Dose-finding Induction study.
- 33 If the Week 8b visit occurs out of window, the dates of subsequent visits will be based on the Week 8b visit start date to ensure a full 8 weeks of treatment in Extended Induction.

Note: See [Appendix 11](#) for general guidance on study conduct during the coronavirus disease 2019 (COVID-19) pandemic. Variations from planned assessments will still constitute protocol deviations.

Table 2: Schedule of Study Procedures – Maintenance Study

Procedures	mWeek 0 ⁽¹⁾	mWeek 4	mWeek 12	mWeek 20	mWeek 28	mWeek 36	mWeek 44	Early Study Drug Discontinuation ⁽²⁾	End of Study ⁽³⁾
Window	+1 to +7 days after Week 8a or 16 visit	-3 to +5 days					-3 to +2 days	+5 days	-3 to +5 days
Review Inclusion/Exclusion Criteria	X ⁽⁴⁾								
Weight	X ⁽¹⁵⁾						X	X	X
Vital Signs ⁽⁵⁾	X	X	X	X	X	X	X	X	X
12-Lead ECG ⁽⁶⁾	X ⁽¹⁵⁾						X	X	X
Physical Examination ⁽⁷⁾	X ⁽¹⁵⁾	X		X			X	X	X
Plasma PK Samples ⁽⁸⁾	X		X		X		X		
Concomitant Medication Review	X	X	X	X	X	X	X	X	X
Adverse Events Assessment ⁽⁹⁾	X	X	X	X	X	X	X	X	X
Pregnancy Test (females of child-bearing potential only) ⁽¹⁰⁾	X	X	X	X	X	X	X	X	X
Chemistry, Hematology	X ⁽¹⁵⁾	X	X	X	X	X	X	X	X
Urinalysis	X ⁽¹⁵⁾						X	X	
Overnight Fasting Lipid Panel	X ⁽¹⁵⁾		X	X	X		X	X	X
[REDACTED]	[REDACTED]	[REDACTED]	[REDACTED]	[REDACTED]	[REDACTED]	[REDACTED]	[REDACTED]	[REDACTED]	[REDACTED]
Endoscopy and Biopsies							X ⁽¹⁷⁾		
[REDACTED]	[REDACTED]			[REDACTED]			[REDACTED]	[REDACTED]	
Whole Blood and Serum Biomarker Samples	X ⁽¹⁵⁾	X			X		X	X	X
Physician Global Assessment (PGA)	X	X	X	X	X	X	X	X	X
Partial Mayo score	X	X	X	X	X	X	X	X	X
Adapted Mayo score							X		
Clinical Flare Assessment ⁽¹²⁾		X	X	X	X	X			
Subject Diary Completion and Compliance Review ⁽¹³⁾	X	X	X	X	X	X	X	X	X
[REDACTED]	[REDACTED]			[REDACTED]			[REDACTED]	[REDACTED]	

Table 2: Schedule of Study Procedures – Maintenance Study

Procedures	mWeek 0 ⁽¹⁾	mWeek 4	mWeek 12	mWeek 20	mWeek 28	mWeek 36	mWeek 44	Early Study Drug Discontinuation ⁽²⁾	End of Study ⁽³⁾
[REDACTED]	[REDACTED]			[REDACTED]			[REDACTED]	[REDACTED]	
[REDACTED]	[REDACTED]			[REDACTED]			[REDACTED]	[REDACTED]	
[REDACTED]	[REDACTED]			[REDACTED]			[REDACTED]	[REDACTED]	
Re-Randomization	X								
Study Drug Dispensing	X	X	X	X	X	X			
In Clinic Dosing - Study Drug Dosing	X ⁽¹⁾						X ⁽¹⁴⁾		
Non-Site Study Procedures (Calculations for Programming/Statisticians and applicable suppliers)									
Partial Mayo score and PRO2 score calculation	X	X	X	X	X	X	X	X	X
Adapted Mayo score calculation	X						X		

Abbreviations: ECG, electrocardiogram; EOS, End of Study; [REDACTED]; PK, pharmacokinetic; PRO2, two-item patient reported outcome; [REDACTED]; [REDACTED]; [REDACTED]; LTS, Long Term Safety Study, (Protocol 0164); EOS, End of Study

Maintenance Studies:

1. Subject should be instructed to not take their allocated Induction Study drug at home on mWeek 0 to allow for in-clinic administration of the Maintenance study drug at this visit.
2. This visit is for subjects who prematurely discontinue the Study drug during the Maintenance phase and are not eligible for the 0164 LTS study. This visit will be conducted within 5 days of the last dose of Study drug. Subject will also return for the EOS visit for collection of safety data and assessment of disease activity four weeks after last study drug.
3. The EOS visit is only applicable to subjects who do not proceed to the 0164 LTS study.
4. Subject will be reassessed for inclusion specific to Maintenance Study.
5. Blood pressure and heart rate will be measured after the subject has been resting for at least 5 minutes in the seated or supine position. Vital sign measurements should be obtained prior to scheduled blood draws.
6. ECGs must be performed after the subject has been resting in a supine position for at least 10 minutes. ECG at mWeek0 needs to be performed only if none performed within the prior 14 days.
7. Physical Exam will be performed in accordance with local standard practice. (Section 6.4.1.19).
8. PK sampling will be performed in subjects at the following time points:

- a. **mWeek 0** (n =2 samples): **One predose** and **one postdose** sample collected any time between 0.5 and 6 hours
 - b. **mWeek 12** and **mWeek 28** (n = 1 sample): One sample to be collected **anytime** during the clinic visit
 - c. **mWeek 44** (n = 3 samples): **one predose**, and **two postdose samples** collected any time between 0.5 and 6 hours postdose and separated by at least 1 hour. **NOTE:** this PK sample should be obtained either **prior** to subject receiving bowel prep for endoscopy or **>24** hours post bowel prep
Predose samples will be taken within 1 hour prior to Study drug administration. Postdose sampling times are defined relative to the time of Study drug administration on the day of collection. All PK sampling times will be accurately recorded by collection date, hour, and minute. Study drug dosing time on the day **before each** PK collection will also be accurately recorded by dosing date, hour, and minute by the subject; Study drug dosing time on the day of each PK collection will be accurately recorded by dosing date, hour, and minute by the Study staff if drug is administered in the clinic or by the subject if drug is administered outside of the clinic.
9. AE assessments are to include collection and reporting of AEs, SAEs, and AEs of Special Interest (AESIs). Please refer to protocol Section 7 for further details.
 10. Urine b-hCG testing will be performed before dosing when dosing in-clinic and anytime during all other visits for females of childbearing potential to confirm absence of pregnancy. If urine b-hCG test is positive, confirm with serum b-hCG test.
 11. Fecal samples may be collected within 3 full days (approximately 72 hours) of the respective visits up to the end of the day following the visit (but before bowel preparation) and has to be delivered to the study site within 24 hours. It is preferable that these stool samples be collected during the first bowel movement in the morning.
 12. Refer to Section 6.3.12 for further details on Clinical Flare Assessment Visits
 13. Diaries of symptoms will be collected daily. Diary completion will be monitored for completeness at each Study visit. Subjects will be counseled on missed Study drug doses and missed diary entries. Subjects who discontinue study drug early due to AE are permitted to optionally complete their daily diary through to the EOS visit.
 14. Study drug administration will be in-clinic on mWeek 44 visit after all pre-dose assessments [mWeek 44: All blood tests need to be collected and procedures have been completed prior to dose (except for post-dose PK blood collection and [REDACTED], which may be done post--visit)]. Subject will take the Study drug at home for the rest of the Study (including Clinical Flare Assessment Visits). On days of endoscopy (mWeek and Clinical Flare Assessment Visit 2, if applicable), study drug can be administered before or after endoscopy; if done before endoscopy, study drug will be taken with whatever the volume of water is allowed by the endoscopy team before endoscopic sedation.
 15. Applicable assessments should be done only if not done within the prior 14 days.
 16. [REDACTED].
 17. The centrally read endoscopic subscore will be used for all endpoints and for eligibility criteria to enroll a subject into the Long-Term Safety Study. Local reading of the endoscopic subscore will also be collected.

Note: See [Appendix 11](#) for general guidance on study conduct during the coronavirus disease 2019 (COVID-19) pandemic. Variations from planned assessments will still constitute protocol deviations.

Table 3: Schedule for Clinical Flare Assessment Visits

Procedures	CFA Visit 1 ⁽¹⁾	CFA Visit 2 ⁽¹⁾	CFA Visit 3 ^{(1) (2)}
Window	0 to 14 days of initial reporting	0 to 14 days after CFA Visit 1	8 weeks after CFA Visit 1 (window -3 to +5 days)
Vital Signs	X ⁽⁵⁾		X
Physical Examination	X ⁽⁵⁾		X
Concomitant Medications	X	X	X
Adverse Events Assessment	X	X	X
Chemistry, Hematology	X ⁽⁵⁾		X ⁽³⁾
[REDACTED]	[REDACTED]		[REDACTED]
[REDACTED]	X		
ECG			X ⁽³⁾
Endoscopy		X	
PGA to calculate partial Mayo score	X		X
Adapted and total Mayo scores		X	
Subject Diary Completion and Compliance Review	X	X	X
[REDACTED]			[REDACTED]
[REDACTED]			[REDACTED]
[REDACTED]			[REDACTED]
[REDACTED]			[REDACTED]

Abbreviations: CFA; Clinical Flare Assessment

1. Refer to Section 6.3.12 for further details
2. Allowed window - 3 to + 5 days approximately 8 weeks after CFA Visit 1, i.e., within 10 weeks after initial reporting of symptom worsening.
3. These only need to be completed during the CFA visit 3 if subjects meet criteria to discontinue from study drug administration.
4. Stool can be collected up to 72 hours before to the end of the day following this visit. If investigator deems stool should be sent for infectious evaluation, that can be done, but it is not required.

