Upon completion of the analyses based on the Phase 2b Induction data, the sample size may be refined. Currently, it is estimated that 320 subjects per dose group (640 subjects total) will provide at least 90% power to demonstrate the selected TD-1473 dose is effective compared to placebo for the primary endpoint of clinical remission at Week 8 under the following assumptions:

- Type 1 error rate of 5% (2-sided tests)
- Clinical remission rate of 9.5% for placebo at Week 8
- Clinical remission rate of 23.5% for TD-1473 at Week 8

If two TD-1473 doses are selected, then 320 subjects per group will have 90% disjunctive power to demonstrate at least one of the two TD-1473 doses is effective compared to placebo for clinical remission at Week 8 under the following assumptions:

- Hochberg step up procedure adjustment for multiple comparisons
- Family-wise type 1 error rate to be controlled at 5% (2-sided)
- Clinical remission rate of 9.5% for placebo at Week 8
- Clinical remission rate of 23.5% for the more effective TD-1473 dose and 16.5% for the less effective TD-1473 dose.

For the Phase 2 and Phase 3 Inductions studies, subjects will be stratified by prior biologics failure and baseline corticosteroids use at randomization. In addition, randomization caps will be placed on both prior biologics failure subgroups (no to biologics failure [60%] and yes to biologics failure [60%]) to ensure that neither subgroup is overrepresented.

Phase 3 Maintenance Sample Size Considerations

Upon completion of the analyses based on the Phase 2b Induction data, the sample size may be refined. Currently, it is estimated that 120 subjects per dose group (360 subjects total) will provide at least 90% disjunctive power to demonstrate at least one of the two TD-1473 doses is effective compared to placebo for the primary endpoint of clinical remission at Maintenance Week 44 under the following assumptions:

- Hochberg step-up procedure adjustment for multiple comparisons
- Family-wise type 1 error rate to be controlled at 5% (2-sided)
- Clinical remission rate of 15% for placebo at Week 44
- Clinical remission rate of 30% and 40% for the two active TD-1473 doses at Maintenance Week 44

A total of 360 subjects total will provide 80% conjunctive power to demonstrate both doses of TD-1473 are effective compared to placebo for clinical remission at Maintenance.

Study Endpoints:

Phase 2b Induction Primary and Secondary Efficacy Endpoints:

Primary:

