8.2. Sample Size and Power

It is currently estimated that approximately 880 subjects (240 for Phase 2b Induction and 640 for Phase 3 Induction) will be enrolled.

The number of enrolled subjects is expected to provide at least 90% power for the primary endpoints of the Induction Studies and also allow a sufficient number of subjects eligible for re-randomization into the Phase 3 Maintenance Study because:

1. A subset of subjects from the initial Phase 3 Maintenance study before final dose selection is determined will be excluded from the analysis of primary and secondary efficacy endpoints: i.e., the subjects assigned to doses that were not selected.
2. Only subjects who received TD-1473 and are considered responders after 8 weeks of Induction therapy, including subjects who are randomized to placebo during the first 8 weeks of Induction Therapy who demonstrate clinical response at Week 16 after receiving TD-1473 80 mg from Weeks 9 to 16, are eligible to be re-randomized in the Phase 3 Maintenance study.
3. The average responder rate for the active treatment groups is estimated to be 60%.
4. It is also estimated that approximately 10% of subjects who are eligible to be re-randomized into the Phase 3 Maintenance study will elect not to participate.

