8.2.2. Induction Phase 3 Sample Size Considerations

Upon completion of the analyses based on the Phase 2b Induction data, the sample size may be refined. Currently, it is estimated that 320 subjects per dose group (640 subjects total) will

provide at least 90% power to demonstrate TD-1473 is effective compared to placebo for the primary endpoint of clinical remission at Week 8 under the following assumptions:

- Type 1 error rate of 5% (2-sided)
- Clinical remission rate of 9.5% for placebo at Week 8
- Clinical remission rate of 23.5% for TD-1473 at Week 8:

It is also estimated that 320 subjects per group will provide at least 90% power to demonstrate TD-1473 is effective compared to placebo for the key secondary endpoints of symptomatic remission and endoscopic healing.

In the case where two TD-1473 doses are selected, then 320 subjects per group will have at least 90% disjunctive power to demonstrate at least one of the two TD-1473 doses is effective compared to placebo for clinical remission at Week 8 under the following assumptions:

- Hochberg step up procedure adjustment for multiple comparisons
- Family-wise type 1 error rate to be controlled at 5% (2-sided)
- Clinical remission rate of 9.5% for placebo at Week 8
- Clinical remission rate of 23.5% for more effective TD-1473 dose and 16.5% for the less effective TD-1473 dose

Subjects will be stratified by prior biologics failure and baseline corticosteroids use at randomization. In addition, randomization caps will be placed on both prior biologics failure subgroups (no to biologics failure (60%) and yes to biologics failure (60%)) to ensure that neither subgroup is overrepresented.

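### The synopsis states a flat 90% disjunctive power for two doses at 320 per group in Phase 3 Induction; its own assumptions give about 99.7%, and Section 8.2.2 states the same case only as a floor.

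*Protocol*

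**What the plan says.** The protocol synopsis, under Phase 3 Induction Sample Size Considerations, covers two cases.

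- **One dose, the planned case:** "320 subjects per dose group (640 subjects total) will provide at least 90% power", with remission of 9.5% on placebo and 23.5% on TD-1473.
- **Two doses, a contingency:** "320 subjects per group will have 90% disjunctive power to demonstrate at least one of the two TD-1473 doses is effective compared to placebo". The placebo rate is again 9.5%, and the dose rates are 23.5% and 16.5%. The multiplicity rule is "Hochberg step up procedure adjustment for multiple comparisons" at a two-sided family-wise 5%.

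Section 8.2.2 repeats the two-dose case with the same size, rates, procedure and error rate, but there "320 subjects per group will have at least 90% disjunctive power".

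Both places say the sample size may be revised once the Phase 2b data are in. Section 8.2 gives two purposes for total enrolment: at least 90% power for the Induction primary endpoints, and to "also allow a sufficient number of subjects eligible for re-randomization into the Phase 3 Maintenance Study". For Maintenance, the synopsis and Section 8.2.3 report disjunctive and conjunctive power together. For two-dose Induction only disjunctive power is reported.

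**The concern.** A flat power figure tied to a stated size, with every assumption listed, should reproduce. This one does not, and the gap of nearly 10 percentage points is too large to be rounding or a choice of variance formula.

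Two things follow. The same section says the size may be refined after Phase 2b, and anyone who scales from 320 per group as the size that gives 90% starts from a base about twice too large for that power. Also, a bare 90% for at least one dose tells the reader nothing about the weaker dose, where this design is much less secure.

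**Working it through.** **Inputs.** From the synopsis: 320 per group, rates 0.095, 0.235 and 0.165, Hochberg over two comparisons with placebo, two-sided 0.05. Section 8.5.4 specifies a stratified CMH test. No stratum rates are given, so an unstratified two-proportion z-test stands in for it. No dropout inflation is stated; missing outcomes count as failures.

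**Calibration on the plan's other figures.** The same simulation approach gives, for Phase 2b, 88.9% for all three doses and 98.4% for at least one at SD 3 (plan: 89% and more than 98%), and 73.8% and 93.8% at SD 3.5 (plan: 73% and 94%). For Maintenance at 120 per group it gives 80.3% conjunctive (plan: 80%). So the method recovers the sponsor's exact figures where they are given.

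**Closed-form check at 320 per group.** Power ≈ Φ((Δ − z·SE₀)/SE₁), where SE₀ uses the pooled variance and SE₁ the unpooled variance.

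- Higher dose: Δ = 0.14; SE₀ = √(2 × 0.165 × 0.835/320) = 0.02934; SE₁ = √((0.095 × 0.905 + 0.235 × 0.765)/320) = 0.02882.
  - At 0.05: (0.14 − 1.960 × 0.02934)/0.02882 = 2.86, power 99.8%. This is also the one-dose case.
  - At 0.025: (0.14 − 2.241 × 0.02934)/0.02882 = 2.58, power 99.5%.
- Lower dose: Δ = 0.07; SE₀ = √(2 × 0.13 × 0.87/320) = 0.02659; SE₁ = √((0.095 × 0.905 + 0.165 × 0.835)/320) = 0.02644.
  - At 0.05: (0.07 − 1.960 × 0.02659)/0.02644 = 0.68, power about 75%.

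Hochberg rejects at least one hypothesis whenever the smaller p-value is at most 0.025. Disjunctive power therefore cannot fall below the higher dose's 99.5%, which already rules out 90%.

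**Simulation.** Three binomial arms with a shared placebo arm, 400,000 trials per case, pooled z-test. Hochberg rejects both if both p ≤ 0.05, otherwise the smaller if p ≤ 0.025.

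| n per group | At least one dose | Both doses |
|---|---|---|
| 160 | 89.7% | 45.6% |
| 162 | 90.2% | 46.1% |
| 213 (640 over three arms) | 96.4% | 57.5% |
| 320 | 99.7% | 75.6% |

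Power for the lower dose alone at 320 per group is also 75.6%, because the higher dose almost always succeeds when the lower one does. With continuity correction, 320 per group gives 99.5–99.6% disjunctive and about 72% conjunctive, and 90% disjunctive power is reached at about 175 per group.

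**Attempts to recover 90% at 320 per group.** Unpooled variance gives 99.7%. Assumed losses of 10%, 20% and 30% counted as failures give 99.2%, 98.2% and 96.3%. None of these readings reaches 90%.

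**The case against.** The strongest reply is that a qualifier was dropped and no calculation went wrong. Section 8.2.2 states the same case with the qualifier, the synopsis sends the reader to Section 8 for details, and the one-dose and Maintenance sentences are floors too. Maintenance disjunctive power at 120 per group is about 99.0%, also reported as at least 90%. This stands as the likely explanation, and it means Section 8.2.2 is correct as a floor. It does not make the synopsis sentence true.

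The consequences are limited. Sections 2 and 3.1 plan for one Induction dose; two doses are a contingency. The Maintenance SAP (Section 1) records that Maintenance was stopped early for lack of efficacy in Phase 2b and that the abbreviated report covers only those two studies, so no analysis in the SAPs rests on this sentence. It is also fair to say that the contingency aims at one effective dose, so leaving out conjunctive power is not an arithmetic error. The case for adding it is consistency with Maintenance and usefulness for any re-sizing.

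A reader might infer that the Maintenance feed alone sets 320 per group. The documents do not support that. Section 8.2 names Induction power and the feed jointly, and Section 8.2.2 adds at least 90% power for two key secondary endpoints whose rates are not given. The feed estimate of about 400 eligible subjects in Section 8.2.3 also rests on 880 enrolled, the one-dose design. Take 60% response to active drug (applied also to placebo non-responders switched to 80 mg), 10% refusal (both from Section 8.2) and an assumed 30–40% placebo response. One dose then gives 0.9 × (500 × 0.6 + 380 × 0.6 to 0.7 × 0.6) ≈ 393–414. Two doses at 320 per group put 960 in Phase 3 and raise this to about 566–586.

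**Conclusion.** The two-dose power in the synopsis is wrong as written: about 99.7% against a stated 90%, with 90% belonging to about half the stated size. The error is minor and errs on the conservative side. The result rests on the plan's own rates and an unstratified z-test in place of CMH; stratification would not plausibly bring 99.7% near 90%. Conjunctive power is about 76%, or about 72% with continuity correction.

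Three stronger conclusions might be drawn, and none holds. The study is not underpowered for its stated aim. Section 8.2.2 does not conceal anything; it is imprecise. And the finding is no argument for cutting to 160 per group, where power for both doses would fall to about 46%. The one-dose statement is a true floor and needs no correction.

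**What to change.** In the synopsis, and in Section 8.2.2 for consistency, give the two-dose power at 320 per group as about 99.7% disjunctive, with about 76% conjunctive beside it, in the format already used for Maintenance. At minimum, insert the missing *at least* in the synopsis so that it agrees with Section 8.2.2. Leave the sample size as it is, and do not add a statement that Maintenance re-randomisation alone determines it.

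The cost is wording only. The one drawback for the sponsor is that the conjunctive figure looks less favourable than a lone disjunctive one.
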